#### **D. Treatment**

Patients will be stratified for randomization on the basis of HBeAg status and on the basis of previous therapy. The primary study will be in patients (Groups A and B) who have not been previously treated (treatment naïve) and who have active liver disease (based on ALT levels and liver biopsy) and high levels of HBV DNA ( $>10^4$  IU/ml). The salvage study will be in patients (Groups C and D) who have received other nucleoside analogues and who continue to have HBV DNA detectable in serum ( $>10^2/10^3$  IU/ml, respectively). A total of 100 patients will be enrolled including at least 60 patients total in Groups A and B and up to 40 patients in Groups C and D (previously treated).

**Group A:** Up to 20 patients with detectable HBeAg in serum and no previous therapy with nucleoside analogues.

**Group B:** Up to 20 patients without detectable HBeAg in serum and no previous therapy with nucleoside analogues.

**Group C:** Up to 20 patients who have previously received lamivudine, adefovir or entecavir therapy but who have persistence of HBV DNA in serum as detected by PCR-based assay ( $>10^2$  IU/ml) and HBeAg in serum for at least six months.

**Group D:** Up to 20 patients who have previously received lamivudine, adefovir or entecavir therapy but who have persistence of HBV DNA in serum as detected by PCR-based assay ( $>10^2$  IU/ml) and absence of HBeAg in serum for at least six months.

**Group E:** Up to 20 patients who have previously received lamivudine, adefovir or the combination of lamivudine and adefovir and who relapsed after therapy was stopped

After medical evaluation, liver biopsy and informed written consent, patients will be randomized in double-blind fashion to receive either combination therapy with tenofovir and emtricitabine or mono-therapy with tenofovir. Patients with anti-viral resistance to lamivudine adefovir, entecavir or telbivudine or multi-drug resistance will continue on pre-study medication until the day of randomization. Randomization will be done by random numbers kept by the Pharmaceutical Developmental Service of the Clinical Center (A1-20, B1-20, C1-20, D1-20, E1-20). Both tenofovir (300 mg tablets) and Tenofovir (300 mg) / emtricitabine (200 mg) will be provided by Gilead Sciences. A 12 week supply of medications will be provided. Compliance will be monitored by medication diaries and counting of the residual tablets returned at outpatient visits.

Patients will be seen in the outpatient clinic at weeks 0, 2, 4, 8, 12, 24, 36, and 48 weeks during the first year of therapy and at 12 week intervals thereafter.

At 48 weeks, all patients will be readmitted to the NIH Clinical Center and undergo a repeat thorough medical evaluation and liver biopsy. Patients in the salvage arm will be excluded from undergoing the 48 week liver biopsy. Continuation of therapy thereafter will depend upon both tolerance and benefit. All patients will undergo a 192 week follow-up biopsy to assess long-term efficacy and durability of response. Benefit is described in Section F “Assessment of Response” and tolerance in Section G “Assessment of Toxicity.”

The side effects will be monitored regularly. Tenofovir and emtricitabine will be stopped if moderate side effects attributable to either or both medications develop and persist for at least one week or on repeat testing. The medication(s) can be restarted if the adverse event resolves and does not appear to be related to either or both medications.

In the absence of toxicity attributable to either agent, combination therapy with tenofovir and emtricitabine or monotherapy with tenofovir will be continued for 192 weeks. Study medication/s will be discontinued if there is serological evidence of resolution of chronic hepatitis B, as shown by loss of HBsAg, documented on two serum samples taken at least six months apart.

Patients on therapy who develop evidence of drug resistance with elevations of serum aminotransferase levels twice above normal and HBV-DNA levels greater than  $10^6$  IU/ml will be switched to alternative therapies if mutually agreed between the patient and the investigators.

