### Précis

Chronic hepatitis B is a major cause of cirrhosis, end-stage liver disease and hepatocellular carcinoma and affects approximately 1.25 million Americans. Six medications have been licensed for use in chronic hepatitis B in the United States, but their relative benefit and long-term efficacy remain unclear. In previous studies, we have shown that maintained suppression of HBV DNA can be achieved with nucleoside analogues and that suppression is associated with marked improvements in disease. In this randomized study, we propose to evaluate long-term therapy with tenofovir alone or in combination with emtricitabine (FTC). Forty treatment-naïve patients with chronic hepatitis B will be enrolled in the primary study. After medical evaluation and liver biopsy, patients will be stratified by hepatitis B e antigen (HBeAg) status and randomized to receive either tenofovir alone or in combination with FTC. Treatment will be continued long-term (at least four years) and patients will be carefully monitored for side effects, serum aminotransferase and HBV DNA levels. Patients will undergo repeat liver biopsy and assessment of antiviral resistance at 1 and 4 years. The primary endpoint of therapy will be the maintained suppression of HBV DNA to below  $10^2$  IU/ml (lower limit of detection of current assays). The study will assess the relative efficacy and safety of combination versus mono-therapy. A separate group of 60 previously treated patients will also be enrolled and randomized to mono- or combination-therapy to assess the safety profile of these agents. The primary analysis will be conducted on the entire study cohort.

[Word count = 250]

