term maintenance therapy for patients with chronic hepatitis B (both HBeAg-positive and -negative). The results of this trial will be compared to historical controls from a NIH trial evaluating the combination of lamivudine and adefovir versus adefovir monotherapy and published multicenter randomized control trials of lamivudine and adefovir for HBeAg positive chronic hepatitis B. The primary endpoint of this trial will be a maintained suppression of HBV DNA below  $10^2$  IU/ml and secondary endpoints will be normalization of serum ALT levels and improvement in histological features of chronic hepatitis. A separate group of patients will be treated with either tenofovir alone or tenofovir and emtricitabine as a “salvage” protocol for patients who have received nucleoside analogue therapy and have failed to have complete viral suppression despite at least 48 weeks of therapy or who have relapsed following withdrawal of therapy. This “salvage” arm will allow for further evaluation of safety and viral suppression and will be used in the primary analysis of response to tenofovir monotherapy vs. combination therapy of tenofovir and emtricitabine.

**Hypotheses and Issues:** This protocol will address the following questions.

Treatment naïve patients:

1. Will combination therapy using tenofovir and emtricitabine have superior antiviral effects against HBV compared to tenofovir alone? To address this issue, HBV DNA and ALT levels will be monitored frequently and both the absolute decrease and the slope (kinetics) of decrease will be compared. The investigators believe that the patterns of decrease of HBV DNA and ALT levels will be similar between tenofovir and combination arms, the pattern reflecting the more potent activity of tenofovir and the absence of a synergy or additive effect of these two nucleos(t)ide analogues.
2. Will combination therapy prevent or delay the appearance of antiviral resistance to tenofovir? To address this issue, the HBV polymerase gene will be sequenced from all serum samples at yearly intervals that are HBV DNA positive. Rates of development of mutations shown to be associated with tenofovir resistance (rtA194T) will be compared between the combination and monotherapy arms. The investigators believe that the rate of antiviral resistance will be low and that at 4 years, 20-25% of patients in the monotherapy arm but no patients in the combination arm will exhibit genotypic antiviral resistance.

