### Protocol

Up to 100 patients with chronic hepatitis B will be enrolled including at least 40 patients who have not been previously treated (naïve patients: primary study) and up to 40 patients who have received or are receiving nucleoside analogue therapy and up to 20 patients who have relapsed following withdrawal of therapy (experienced patients: salvage study). After medical evaluation and liver biopsy, patients will be randomized and receive either monotherapy with tenofovir (300 mg) daily or combination therapy with tenofovir (300 mg) and emtricitabine (FTC: 200 mg) daily. Gilead Sciences will provide the combination of tenofovir and emtricitabine as a single tablet and tenofovir 300 mg as a single tablet. Neither the investigators nor the patients will be blinded to the investigational agents. Patients will be followed carefully on therapy at 2 to 12 week intervals and undergo repeat medical evaluation and liver biopsy at 48 and 192 weeks. Therapy will be continued indefinitely, although the randomized phase of this trial will last for 192 weeks only. The definition of a successful endpoint of therapy will be the maintained suppression of HBV DNA below  $10^2$  IU/ml by current PCR-based assays, Roche Amplicor assay). Secondary endpoints will be (2) normalization of ALT levels and (3) histological improvements which are expected to occur in all patients with full suppression of HBV DNA and in a proportion of those with partial suppression. Other endpoints will be (3) loss of HBeAg and (4) loss of HBsAg. Patients who have lost HBsAg will undergo a monitored withdrawal of therapy with reinstatement of treatment if relapse occurs.

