#### A2. Inclusion criteria: Salvage Study (nucleoside analogue experienced subjects)

- 1) Age >18 years and older, male or female
- 2) Known serum HBsAg positivity for 6 months

- 3) Detectable **HBV DNA >10^2** IU/ml.
- 4) Liver biopsy within 5 years of entry that is consistent with chronic hepatitis
- 5) Written informed consent

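### Section D asks for at least 60 treatment-naive patients, but its own group caps and randomisation lists hold only 40, and its breakdown of the 100 omits Group E

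*Combined protocol and SAP*

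**What the plan says.** The enrolment numbers appear in four places.

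- **Précis:** forty naive patients form the primary study, and "A separate group of 60 previously treated patients will also be enrolled and randomized".
- **Protocol (opening paragraph):** up to 100 patients, "including at least 40 patients who have not been previously treated", with up to 40 who have had or are on nucleoside analogues and up to 20 relapsers.
- **D. Treatment:** the total of 100 is broken down as "including at least 60 patients total in Groups A and B and up to 40 patients in Groups C and D (previously treated". The group definitions that follow cap each of Groups A, B, C, D and E at 20. The lists held by the pharmacy service are "A1-20, B1-20, C1-20, D1-20, E1-20".
- **I. Statistical analysis:** the primary analysis covers the entire cohort, identified in brackets as Groups A to D. Fisher's exact test, two-sided at 0.05, is said to have 86% power for 94% against 70% with 50 per arm.

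Two related places bear on who can be given a list number. The Background, at the end of the section on the choice of tenofovir and FTC, describes salvage patients as those who "have failed to have complete viral suppression despite at least 48 weeks of therapy", or who relapsed after withdrawal. Section A2, headed "Inclusion criteria: Salvage Study (nucleoside analogue experienced subjects", sets no duration of earlier treatment and names no earlier drug. Section A.3, for relapsers, names no drug either.

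**The concern.** The sentence in section D is an operational rule: it tells staff how many patients of each kind to recruit. It cannot be followed with the lists printed in the same section, because the naive lists run out at the 40th patient while the rule asks for at least 60. It also accounts for all 100 patients without mentioning Group E.

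Two things depend on the numbers. The naive cohort is called the primary study, but naive and treated patients are pooled in the primary analysis, so the split decides which population the pooled result mainly describes. The naive share is 40% under the Précis and the lists, and at least 60% under the section D sentence. The split also determines how many patients Groups A to D contain, and section I uses those groups to define the primary cohort.

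**Working it through.** **Inputs.** The caps and lists in section D are 20 each for A, B, C, D and E. The section D sentence gives a total of 100, A+B at least 60, and C+D at most 40. The Précis gives 40 naive and 60 treated. The Protocol section gives naive at least 40, experienced at most 40, and relapsers at most 20. Section I gives 0.94 against 0.70, two-sided alpha 0.05, and 50 per arm.

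**Step 1: the naive minimum against the caps.** A+B is at most 20 + 20 = 40. The sentence needs 60, so the shortfall is 60 − 40 = 20 allocation numbers. Enumerating every combination with A+B ≤ 40, C+D ≤ 40 and E ≤ 20 gives none with A+B ≥ 60.

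**Step 2: what the caps do allow.** The caps sum to 40 + 40 + 20 = 100. A total of 100 is reached in one way only, with every list full: 40 naive, 40 experienced, 20 relapsers. That is 40 naive and 40 + 20 = 60 previously treated, as in the Précis. The Protocol section is compatible with this, although it words the naive number as a minimum while the caps make 40 a maximum.

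**Step 3: the stated power.** Power is the sum, over all pairs (x, y), of Bin(x; n, 0.94) × Bin(y; n, 0.70), counting only the pairs for which the two-sided Fisher p-value is at most 0.05.

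| Primary cohort | Patients | Per arm | Exact power |
|---|---|---|---|
| As sized in section I | 100 | 50 | 85.7% (stated 86%) |
| Groups A to D under 40/40/20 | 40 + 40 = 80 | 40 | 76.8% |

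The plan's 86% is reproduced at 50 per arm. Groups A to D reach 100 only under the 60 + 40 sentence, which step 1 shows cannot be carried out.

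**Step 4: eligibility against lists.** Groups C and D are defined by earlier lamivudine, adefovir or entecavir, and Group E by earlier lamivudine, adefovir or both. Sections A2 and A.3 restrict no drug. A patient treated only with telbivudine can therefore meet A2, and an entecavir relapser can meet A.3, yet neither fits a group that has a list. The documents give no basis for estimating how many such patients there would be. Separately, the 48 weeks of earlier therapy in the Background has no counterpart in A2.

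**The case against.** The strongest reply is that this is one outlying sentence. The Précis, the caps and the lists agree on 40 naive and 60 treated, the Protocol section is compatible with that, and the lists govern allocation in practice. This stands, and it rules out several stronger readings that a reader might infer:

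- *The naive/experienced mix is undetermined.* It is stated inconsistently. Only 40/40/20 reaches 100 under the caps.
- *60 + 40 forces Group E to zero.* The 40 is an upper limit, and 60 + 20 + 20 is also 100. What holds is that the sentence omits Group E.
- *The 86% power is wrong.* The calculation uses one rate per arm and does not depend on the mix. It is right for 100 patients analysed.
- *Section D sets a conflicting HBV DNA threshold for Group D.* The paired values in section D match A2 and A.3, so they most plausibly refer to those two salvage populations. The A2 threshold and the Group C and D lines agree.
- *Groups C and D set a six-month minimum of earlier therapy.* The six months describe how long the viral markers have persisted or been absent, not time on treatment. The only duration mismatch shown is between the Background and A2.

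The reply does not remove the contradiction inside section D. Nor does it deal with section I, whose 50 per arm over Groups A to D agrees with the faulty sentence and not with the lists.

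**Conclusion.** The section D sentence is wrong as written. Its naive minimum exceeds the available places by 20, it contradicts the Précis, and it omits Group E. The defect is in a stated enrolment figure, and the intended split can be recovered from the rest of the protocol. No bias in the treatment comparison has been shown.

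The consequence that can be quantified is in section I. If Group E is outside the primary analysis and the lists fill, 80 patients are analysed and power is about 77% instead of 86%. If Group E is inside, the 86% stands. These figures assume equal allocation, all lists filled, and the plan's own response rates of 94% and 70%.

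The eligibility mismatches in step 4 are secondary. They are real in the text, but their effect on numbers is unknown.

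**What to change.** 1. In section D, replace the 60/40 sentence with 40 patients in Groups A and B, 40 in Groups C and D, and 20 in Group E, total 100. In the Protocol section, change the naive minimum of 40 so that it agrees with the caps of 20 each.
2. In the same amendment, reconcile section I. If 50 per arm and 86% power are intended, name Groups A to E as the primary cohort. If Group E is to be excluded, restate the size as 40 per arm and the power as about 77%.
3. Reconcile the duration of earlier therapy in the Background with A2, and the earlier drugs listed for Groups C, D and E with A2 and A.3, so that every eligible patient has a randomisation list. Which duration and which drugs should apply is for the investigators to decide.

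Items 1 and 2 need wording only: the five lists of 20 stay as they are and no patients are added. The one substantive cost arises if Group E is excluded, when the lower power has to be accepted and stated.

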The primary study endpoints will be a maintained full virological response after 48 weeks and 192 weeks of therapy (the two points of formal statistical analysis). The major secondary endpoint will be absence of a failure of therapy and absence of resistance mutations. Other endpoints to therapy will be loss of HBeAg, loss of HBsAg, normalization of serum ALT, improvements in histology activity index, improvements in hepatic fibrosis, improvement in Fibroscan scores and decrease in HVPg. Other endpoints will be improvement in symptom scores at 48 and 192 weeks.

Failure of therapy may be due to primary non-response, lack of virological response, breakthrough, or relapse, as defined below.

A **primary non-response** is defined as lack of decrease in HBV DNA levels by at least 1  $\log_{10}$  after at least 24 weeks of therapy in the absence of non-compliance.

A **failure in virological response** is defined as failure to suppress HBV DNA below  $10^4$  IU/ml after 48 weeks of therapy in the absence of non-compliance.

A **breakthrough** is defined as a  $\geq 1 \log_{10}$  IU/L increase in HBV DNA level from nadir in two consecutive samples at least one month apart in a patient with an initial full virological response in the absence of non-compliance.

A **relapse** is defined as a rise in HBV DNA levels to above  $10^4$  IU/ml or of ALT to above the normal range after therapy is stopped in a patient who previously had a maintained full virological response.

These definitions are all interlocking but help to define response and non-response rates and whether therapy has a sustained effect.

**Stopping therapy:** Therapy will be continued indefinitely or until one of the following endpoints are reached:

1. **Failure of therapy:** If HBV DNA levels remain consistently  $>10^4$  IU/ml after one year of continuous therapy, patients will be offered alternative therapy or the option to stop therapy. Alternative therapies may include switching to combination therapy if they were receiving monotherapy or switching to entecavir if receiving combination therapy. Patients who fail to respond may also elect to receive a course of peginterferon. These options are available at the NIH Clinical Center on an open-label basis.

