#### **L. Data and Safety Monitoring**

The adequacy of data acquisition and storage and the monitoring of safety in this trial will be done by the principal investigator in collaboration with the associate investigators. Data and safety are reviewed weekly in clinical research rounds by the Liver Diseases Branch, NIDDK. These rounds are separate from regular clinical rounds and consist of review of all study patients including flow sheets of major safety and efficacy measurements without knowledge of which therapy is used. Monitoring of this study will also be conducted by the statistical department of NIDDK who will have knowledge of the patient allocation. Reports of serious adverse events are made to the Clinical Director NIDDK, the IRB, study monitor and the FDA.

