Creatinine Clearance		X								X		X
Ultrasound‡		X								X		X
Liver biopsy		X								X		X
Alpha fetoprotein‡		X								X		X
Immunologic tests		X		X	X		X			X		
Fibroscan‡		X								X		X
Bone mineral density		X								X		X
FTCvsPlacebo/Tenofovir		X	X	X	X	X	X	X	X	X	X	X

\* Pre is the initial evaluation which will be an outpatient clinic visit for those who do not require a pretreatment biopsy and a clinical center admission for those who require a pretreatment liver biopsy.

† Routine bloods include CBC, chemistry-20 panel, serum lactic acid and HBV DNA by quantitative PCR.

‡ Urine tests include standard urine analysis and spot urine protein/creatinine ratio and a pregnancy test for women of child bearing potential.

¶ Extended tests include: INR, alphafetoprotein, HBsAg, anti-HBs, HBeAg and anti-HBe and are measured every 12 weeks.

‡ Ultrasound and fibroscan will be measured every 48 weeks.

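### The protocol calls the trial double-blind and lists a placebo, yet says investigators and patients are unblinded, so masking of symptom, toxicity and compliance judgements is unclear

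*Combined protocol and SAP*

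**What the plan says.** Four places in the combined protocol and SAP describe blinding, and they disagree.

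- Section D (Treatment): "patients will be randomized in double-blind fashion to receive either combination therapy".
- Protocol section: "Neither the investigators nor the patients will be blinded to the investigational agents". The same paragraph gives the supply: "Gilead Sciences will provide the combination of tenofovir and emtricitabine as a single tablet and tenofovir 300 mg as a single tablet".
- Section L (Data and Safety Monitoring): the weekly research rounds look at "flow sheets of major safety and efficacy measurements without knowledge of which therapy is used". The only group said to know the arm is the "statistical department of NIDDK who will have knowledge of the patient allocation".
- Appendix A flow sheet: the medication row is labelled "FTCvsPlacebo/Tenofovir". No placebo appears in the treatment or supply text.

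Several outcomes involve judgement. Section F lists a patient-reported one: "Other endpoints will be improvement in symptom scores at 48 and 192 weeks". It also attaches a condition that the patient was compliant to primary non-response, failure in virological response and breakthrough, but not to relapse. Section H attaches a similar condition to phenotypic tenofovir resistance. Section D stops drug for moderate side effects judged attributable to it, and Section F counts stopping for toxicity as failure of therapy. Absence of failure and of resistance mutations is the major secondary endpoint.

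Two outcomes have protection of their own. The primary endpoint is HBV DNA below 10^2 IU/ml by PCR. Section C has biopsies scored by a pathologist who does not see the clinical information.

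**The concern.** Double-blind is a stated property that a reader of the results would rely on. If the trial is in fact open-label, a report could cite Section D for a protection that the Protocol section denies. Differences in symptom scores or in attributed side effects would then be read as masked comparisons when they are not.

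The compliance clauses are the subtler problem. They let someone decide that a virological failure does not count because the patient did not take the drug. Section D monitors compliance by diaries and tablet counts, but the plan sets no numerical threshold. The Hypotheses section also says in advance that the investigators expect response above 90% on the combination and that those who do not respond will probably be non-compliant. A judge who knows the arm and holds that expectation could excuse failures unevenly.

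**Working it through.** **1. Which reading the text supports.**

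| Place | Points to |
|---|---|
| Protocol section, blinding sentence | open-label, stated outright |
| Protocol section and Section D, supply | open-label: two different single tablets, no placebo, matching or over-encapsulation described |
| Section F, options after failure | open-label: they differ by assigned arm (weaker evidence, since a blinded trial may unblind at failure) |
| Section D, randomisation sentence | double-blind |
| Section L, weekly rounds | at least partial masking |
| Appendix A, medication row | placebo-controlled |

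The open-label reading has an explicit statement and a matching supply. The double-blind reading has a label and a row heading, with no described means of delivering either.

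**2. Which outcomes are exposed.**

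- *Primary endpoint.* An assay threshold with no compliance clause. Section I counts missing data and dropout as failure, so nobody can be excused from it. An indirect route remains through dropout and through stopping for side effects judged attributable, because Section F requires a maintained response to be in a patient still on therapy. The documents give nothing from which to size this route.
- *Histology.* Blinded reader in Section C. Section E repeats the initial evaluation at week 48. The masking is not restated for week 192.
- *Symptom scores and attribution of toxicity.* No masking of their own.
- *Failure and phenotypic resistance.* Compliance condition in three of four failure definitions and in the Section H definition.

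**3. The plan's own figure.** Section I gives 86% power for a two-sided 0.05 Fisher's exact test, 94% against 70%, 50 per arm. Power is the sum, over all pairs (i, j) with Fisher p ≤ 0.05, of Bin(i; 50, 0.94) × Bin(j; 50, 0.70). The result is 85.7%, so the figure reproduces. The blinding wording does not enter it.

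**4. An illustration for the compliance-conditional endpoint.** The plan gives no failure rate, test or alpha for this endpoint. I assume the Section I test and size. Let t be the true failure rate, equal in both arms, and e the share of combination failures excused as non-compliant, with none excused on monotherapy. Excused patients stay in the denominator as non-failures, so the counted rates are t(1 − e) and t. The 18% row is the average of the failure rates implied by Section I: (6% + 30%)/2.

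| True failure t | Share excused e | Counted rates (combination v monotherapy) | Chance of p ≤ 0.05 |
|---|---|---|---|
| 18% | 0 | 18% v 18% | 2.7% |
| 18% | 10% | 16.2% v 18% | 3.0% |
| 18% | 20% | 14.4% v 18% | 4.3% |
| 18% | 25% | 13.5% v 18% | 5.3% |
| 18% | 50% | 9% v 18% | 16.5% |
| 6% | 50% | 3% v 6% | 2.1% |
| 10% | 50% | 5% v 10% | 6.3% |
| 30% | 25% | 22.5% v 30% | 9.6% |
| 30% | 50% | 15% v 30% | 35% |

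With t at 18%, the rate stays below the nominal 5% up to about one fifth excused. Larger inflation needs both a high failure rate and a strongly one-sided excuse rate.

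**The case against.** The strongest reply is that little of consequence turns on blinding here. The primary endpoint is a laboratory value, dropouts are failures, biopsies are read blind, and most rules for stopping or switching rest on HBV DNA, aminotransferases or renal measurements. A patient above 10^4 IU/ml is already a non-responder at the 10^2 threshold. Section I plans no formal comparison of symptoms or relatedness. All of this stands, and it is why the point concerns secondary and descriptive outcomes.

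It can also be said that open-label is not proved: the randomisation numbers are held by the pharmacy service, and Section L names only the statistics group as knowing the arm. Pharmacy-held numbers conceal the next assignment but do not mask treatment afterwards, so they fit either design. The documents do not settle the matter, which is itself a reason to reconcile them.

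Three stronger readings are tempting and are not supported:

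- *That the main result has a false-positive rate of about 16%.* That figure is one assumed cell in the table, and it belongs to no test the plan specifies. The primary endpoint has no compliance clause.
- *That nobody is blinded.* The Protocol section speaks of investigators and patients only, and the biopsy reader is masked.
- *That every failure definition turns on compliance.* Relapse does not, and neither do the stopping rule for failure of therapy or failure through toxicity.

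**Conclusion.** The contradiction is real and sits in operative text. Open-label is the better-supported reading, so double-blind is a stated property that the described design does not have. The primary PCR comparison is little affected directly, and histology is protected at baseline and week 48, though this should be restated for week 192. What is left unclear is whether symptom scores, toxicity attribution and its discontinuations, and compliance-conditional failure and resistance are judged masked. The last two bear on the major secondary endpoint.

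The size is not fixed by the documents. Under the assumptions above, false rejection on a compliance-conditional failure comparison runs from about 2% to 35% with half of combination failures excused and true failure of 6% to 30%. It is 3.0% to 5.3% with 10% to 25% excused at 18% true failure. The correction should be made, but the trial's main analysis does not depend on it.

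**What to change.** Reconcile the Protocol section, Section D, Section L and Appendix A so that they describe one design.

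If that design is open-label:

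- Delete the double-blind wording in Section D and the placebo label in Appendix A.
- Limit Section L to what is actually masked, namely flow sheets with treatment removed.
- State that symptom and relatedness comparisons are open-label.
- State that the biopsy reader is masked to arm at week 192 as well.

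If blinding was intended, the unblinded statement must go, and the supply text and Section F must say how masking is achieved and kept.

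Do not rely on the weekly rounds or the statistics group for masked classification. Under the Protocol section the investigators are unblinded, and Section L says the statistics group knows the allocation. Removing a column does not mask people who treat the patients. Take the judgement out instead: analyse failure and resistance regardless of compliance, or set a tablet-count threshold before analysis and apply it identically in both arms.

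The cost is wording, treatment-stripped flow sheets and one analysis rule. Sample size and the 86% power are unchanged.
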